## **2. LIST OF ABBREVIATIONS**

Term	Definition / description
AE	Adverse event
ANCOVA	Analysis of Covariance
AUC	Area under the curve
BI	Boehringer Ingelheim
BMI	Body Mass Index
BRPM	Blinded report planning meeting
COPD	Chronic Obstructive Pulmonary Disease
█	█
CI	Confidence interval
CML	Clinical Monitor Local
CRA	Clinical Research Associate
CT	Concomitant Therapy
CTP	Clinical Trial Protocol
CTR	Clinical Trial Report
DBL	Database lock
EC	Exclusion Criterion
ECG	Electrocardiogram
eCRF	Electronic Case Report Form
EOT	End of treatment
EoT	End-of-text
FDC	Fixed dose combination
FEV 1	Forced expiratory volume in one second
FVC	Forced vital capacity
GCP	Good clinical practice
GOLD	Global Initiative on Chronic Obstructive Lung Disease
H	Hypothesis
IC	Inclusion Criterion
ICF	Informed Consent form
ICH	International Conference on Harmonisation
ICS	Inhaled Corticosteroids
(I)PV	(Important) Protocol violation

Term	Definition / description
IRT	Interactive Response Technology
█	█
LABA	Long Acting Beta Agonists
LOCF	Last observation carried forward
LLT	Lowest level term
Max	Maximum
MI	Myocardial Infarction
Min	Minimum
MMRM	Mixed Model for Repeated Measures
MQRM	Medical Quality Review Meeting
N	Number
NYHA	New York Heart Association
PFT	Pulmonary Function Test
PH	Proportional Hazards
PT	Preferred term
PV	Protocol violation
REML	Restricted maximum likelihood
RR	Rate ratio
RS	Randomized Set
S	Survival distribution
SAS ®	Statistical Analysis Software ®
SD	Standard deviation
█	█
SOC	System organ class
█	█
T+O	Tiotropium bromide and Olodaterol
TIA	Transient Ischemic Attack
Tio	Tiotropium bromide
TS	Treated Set
TSAP	Trial statistical analysis plan
UN(1)	Banded Main Diagonal
AE	Adverse event

[figure not shown]
### **3. INTRODUCTION**

As per ICH E9 (1), the purpose of this document is to provide a more technical and detailed elaboration of the principal features of the analysis described in the protocol, and to include detailed procedures for executing the statistical analysis of the primary and secondary variables and other data.

This TSAP assumes familiarity with the Clinical Trial Protocol (CTP), including Protocol Amendments. In particular, the TSAP is based on the planned analysis specification as written in CTP Section 7 “Statistical Methods and Determination of Sample Size”. Therefore, TSAP readers may consult the CTP for more background information on the study, e.g., on study objectives, study design and population, treatments, definition of measurements and variables, planning of sample size, randomization.

SAS® Version 9.4 will be used for all analyses.

**4. CHANGES IN THE PLANNED ANALYSIS OF THE STUDY**

## **5. ENDPOINT(S)**

### **5.1 PRIMARY ENDPOINT(S)**

The primary endpoint will be used as defined in the revised CTP, Section 5.1.1:

- Annualized rate of moderate to severe COPD exacerbations during the actual treatment period.

The actual treatment period is defined as the interval from first in-take of study medication until 1 day after last in-take of study medication (see [section 6.1](#)).

The definition of a moderate to severe COPD exacerbation is given in Section 5.1.2 of the revised CTP.

### **5.2 SECONDARY ENDPOINT(S)**

#### **5.2.1 Key secondary endpoint(s)**

The key secondary endpoint in this study is defined in the revised CTP, Section 5.1.:

[figure not shown]
- Time to first moderate to severe COPD exacerbation during the actual treatment period.

[figure not shown]
#### **5.2.2 Secondary endpoints**

Secondary endpoints are defined in the revised CTP, Section 5.1. They are:

- Annualized rate of exacerbation leading to hospitalization during the actual treatment period.
- Time to first COPD exacerbation leading to hospitalization during the actual treatment period.
- Time to all-cause mortality occurring during the actual treatment period.

All deaths are adjudicated by a blinded and independent adjudication panel to determine the primary cause of death.

## 6. GENERAL ANALYSIS DEFINITIONS

### 6.1 TREATMENTS

As described in Section 4 of the revised CTP, patients will be randomized in equal allocation to one of two treatment groups delivered by the Respimat® inhaler:

- Tiotropium + olodaterol fixed dose combination (FDC) (5µg / 5µg) inhalation solution once daily
- Tiotropium (5 µg) inhalation solution once daily.

Table 6.1: 1 Treatments and their labels

Treatment	Short label
Tiotropium + olodaterol FDC (5 µg / 5 µg) inhalation solution	T+O 5/5
Tiotropium (5 µg) inhalation solution	Tio 5

The trial consists of a 360 days of treatment followed by a 21 day residual effect period.

For analysis purposes the following periods are defined:

- Planned study period  
The planned study period is defined as 360 days of treatment + 21 days of follow up after the administration of the first dose of trial medication according to the CTP flow chart.
- Planned treatment period  
The planned treatment phase is defined as 360 days of treatment + 1 day for wash-out according to the CTP flow chart.
- Actual treatment period  
The actual treatment period is defined as the interval from first in-take of study medication until 1 day after last in-take of study medication.
- On-treatment period  
The on-treatment period is defined as the interval from first in-take of study medication until 21 days after last in-take of study medication.

Patients that discontinue early will be monitored for exacerbations and vital status until they have reached the end of their planned study period.

Table 6.1:2 Analyses performed within each period

Types of Analyses to be performed	Periods			
	Actual treatment period (Treatment +1 day wash-out)	Planned treatment period (includes 1 day wash-out)	Planned study period (includes residual effect period of 21 days)	On-treatment period (includes residual effect period of 21 days after last drug intake)
Primary Exacerbation analysis	✓			
Sensitivity primary exacerbation analysis		✓		
Key secondary exacerbation analysis	✓			
AE safety analysis				✓

Patients will be analyzed according to the treatment group of the first treatment received. Potential treatment switcher scenarios caused by treatment misallocation will be discussed at the Blinded Report Planning Meeting (BRPM). After database lock (DBL) patients who fall into these discussed scenarios will be analyzed according to meeting decisions.

For the main safety analysis, data occurring during the on-treatment period (as described above) will be assigned to the respective treatment. Adverse events (AEs) occurring before first drug intake will be assigned to ‘screening’. AEs occurring after the 21 day residual effect period will be assigned to the follow-up period (not to any of the treatment arms).

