#### 4.1.4 Drug assignment and administration of doses for each patient

Trial medication will be dispensed to the patient by the investigator/pharmacist. At Visit 2 eligible patients will be randomized to one of two double-blinded treatment arms (1:1 ratio) by the IRT. At subsequent clinic visits (every 3 months), the IRT will assign Respimat® treatment boxes to each patient and each Respimat® treatment box will have a unique number with 6 digits.

One of these Respimat® treatment boxes is a reserve Respimat® inhaler. This reserve kit allows the patient the flexibility of not having to return to the clinic immediately to replace a lost or malfunctioning Respimat® inhaler. In the event that a patient may need additional extra Respimat® inhalers and cartridges due to rescheduled visits, inhaler loss or malfunction, these will be supplied on an 'on demand' basis. Dispensing of these extra Respimat® inhalers will also be managed via the IRT.

Site personnel will enter all medication numbers dispensed to each patient in the Medication Record page of the electronic case report form (eCRF).

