### 4.1.5 Blinding and procedures for unblinding

#### 4.1.5.1 Blinding

Patients, investigators and everyone involved in analysing or with an interest in this double-blind study will remain blinded with regard to the randomised treatment assignments until after database lock.

Boehringer Ingelheim will generate and store the randomisation schedule, and prepare and code the medication in a blinded fashion. Trial supplies will be assigned to the patients via IRT.

Refer to Section 4.1.5.2 for rules of breaking the code in emergency situations.

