### 7.3 PLANNED ANALYSES

#### 7.3.1 Primary analyses

The primary analysis includes all randomised patients who are documented to have received any dose of study medication, i.e., the primary analysis is performed using the treated set.

The primary endpoint, i.e., annualised rate of moderate to severe COPD exacerbation will be analysed using a negative binomial model including the fixed, categorical effect of treatment

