## 7.5 RANDOMISATION

Patients will be randomised in equal ratio to one of the two treatment groups in this trial and blocked randomisation will be used. Boehringer Ingelheim will generate the randomisation scheme and will prepare and code the medications to maintain the double-blind.

In order to maintain flexibility for drug supply, each individual medication kit will have a separate identification number. Assignment of medications at the clinic visits will be accomplished through the use of IRT. Each patient will be assigned a single randomisation number indicating the randomised treatment the patient will be on throughout the trial. BI will provide the randomisation and medication kit number lists to the IRT and the sites will access the IRT to obtain the randomisation number and medication kit numbers to be dispensed to the patient.

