## 6.2 IMPORTANT PROTOCOL VIOLATIONS

A patient’s deviation from the trial protocol is considered “important” if it can be expected that the deviation had a distorting influence on the assessment of the treatment effect on the primary endpoint of the trial or could affect the patient’s safety/rights.

If the Interactive Response Technology (IRT)-assigned randomized medication is not available at the site at the first visit, a forced randomization will occur, and the IRT will assign a treatment that is available at the site. That patient will be assigned within the IRT system to receive that same treatment for the remainder of the trial. Forced randomizations

are part of the study plan and are not classified as important protocol violations. The number of forced randomizations will be closely monitored and described in the clinical trial report.

Table 6.2: 1 Important protocol violations

Category/ Code	Description	Example/Comment	Excluded from	Automatic /Manual
A	Entrance criteria not met			
A1	Inclusion criteria not met	IC 3, 4, 5, 7, 8, 2, 6,	None	Automatic and manual
A2	Exclusion criteria not met	EC 3, 7, 9, 10, 11, 13, 14, 15, 17, 23, 5, 6, 1, 4, 8, 2, 12, 16, 18, 19, 20, 21, 22	Excluded from TS: EC 22 Excluded from none: EC 1-21, 23	Automatic
B	Informed consent			
B1	Informed consent to study not available/not done*		All	Manual
B2	Informed consent too late**		None	Manual
C	Trial medication and randomization			
C1	Incorrect trial medication taken		None	Manual
C2	Randomization order not followed	Date of first trial drug intake prior to randomization date	None	Automatic
C3***	Serious non-compliance with study medication as reported in monitoring report	Decision at BRPM/MQRM.	None	Manual
C4	Medication code broken inappropriately		None	Manual
D	Concomitant medication			
D2	Prohibited medication use during study	Refer to Table 4.2.2.1: 1 in revised CTP.	None	Manual
Z	Other			
Z1	Serious Good Clinical Practice (GCP) non-compliance	Manual PVs reported by CML/CRA or in the GEM system.	None	Manual
Z2	Other PV affecting efficacy and possibly safety		None	Manual

\* Informed consent date missing; no signature on ICF.

\*\* Applies to all informed consents. Date of informed consent was after the date of any study-related procedure.

\*\*\* “Serious non-compliance with study medication” is defined by compliance  $\geq 200\%$  (twice the dose or more).

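### Minor, cheap to improve: SAP 6.1 groups the two confirmatory efficacy tests by first treatment received and leaves misallocation switchers to a blinded meeting; grouping by randomised arm should be fixed in advance

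*SAP*

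**What the plan says.** Directly below the SAP 6.1 table that lists the primary, key secondary and adverse-event analyses, the rule reads "Patients will be analyzed according to the treatment group of the first treatment received". It is not limited to safety. The SAP then adds that "Potential treatment switcher scenarios caused by treatment misallocation will be discussed at the Blinded Report Planning Meeting (BRPM"), and that after database lock "patients who fall into these discussed scenarios will be analyzed according to meeting decisions".

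The other places that describe these tests fix who is analysed and over what period, but not the arm:

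- Protocol 7.3.1 defines the set: "The primary analysis includes all randomised patients who are documented to have received any dose of study medication".
- SAP 6.3 repeats that set and applies it to every analysis.
- SAP 7.4 and 7.5.1 add the actual treatment period. In the SAP 7.4 code the treatment variable is described only as the treatment group.

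The randomised arm is on record. Protocol 7.5 says "Each patient will be assigned a single randomisation number indicating the randomised treatment the patient will be on throughout the trial".

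SAP 6.2 covers forced randomisation. If the "assigned randomized medication is not available at the site at the first visit", the IRT assigns a treatment that is in stock and keeps the patient on it. Wrong trial medication is logged as violation C1 and excludes nobody.

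For adverse events, SAP 7.8.1 refers to the randomised treatment, which is not the SAP 6.1 rule.

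**The concern.** A superiority test draws its validity from comparing groups as randomised. Grouping by receipt is safe only if the reason for receiving the other drug is unrelated to prognosis. Grouping by randomised arm needs no such assumption, and here it is feasible.

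Two parts of SAP 6.1 differ in reach:

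- **The default rule** moves only patients whose first kit at Visit 2 differs from their assignment. A wrong kit at Visits 3 to 5 leaves the default arm unchanged.
- **The meeting clause** is wider. Kits are assigned again later in the trial ("At subsequent clinic visits (every 3 months), the IRT will assign" treatment boxes), so a switcher scenario could include a wrong kit at Visits 3 to 5, and a meeting decision could move that patient too.

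At stake are the arm labels of a probably small number of patients in both confirmatory tests, and a gap in pre-specification.

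**Working it through.** **Inputs.** From protocol 7.6: 3900 per arm, Tio 5 rate 0.85 per year, rate ratio 0.88 (T+O rate 0.748), two-sided alpha 0.01, dispersion 0.625 to 0.9, and a 15% loss of patient-years (T = 0.85; otherwise T = 1). Assumed, because the documents give no figure: misallocation of 0.1%, 0.5% or 1%, and misallocated patients at twice average risk where stated.

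**Formula.** SE(log RR) = sqrt[(1/(T·r1) + d)/n1 + (1/(T·r2) + d)/n2], where d is the dispersion. The test rejects when |log RR|/SE exceeds 2.576.

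**Step 1: reproduce the plan.** With T = 0.85 and d = 0.625:

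- SE = sqrt[(1.3841 + 0.625 + 1.5728 + 0.625)/3900] = 0.0328
- |ln 0.88|/SE = 0.1278/0.0328 = 3.892
- power = Φ(3.892 − 2.576) = 90.6%

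With d = 0.9 the power is 86.1%. With T = 1 it is 93.8% and 89.8%. Protocol 7.6 states 86.1% to 90.6%, and 90% to 94%.

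**Step 2: type I error, expected case (blinded errors).** Simulation under the null with T = 0.85: 78 of 7800 patients (1%), all at twice average risk, receive the opposite of a random assignment. Counts are gamma-Poisson, the test is a Wald test on log RR, and there are 100,000 runs.

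| Dispersion | With errors | No errors |
|---|---|---|
| 0.625 | 0.0103 | 0.0101 |
| 0.9 | 0.0100 | 0.0097 |

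The Monte Carlo SE is 0.0003, so the error rate is nominal.

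**Step 3: type I error, unlikely worst case.** A fraction p of the T+O arm (m = 3900p patients, risk multiple k) is counted in Tio 5. With T = 0.85:

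- T+O rate = 0.85(3900 − mk)/(3900 − m)
- Tio 5 rate = 0.85(3900 + mk)/(3900 + m)

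For p = 1% and k = 2, m = 39. The rates are 0.8414 and 0.8584, so the null RR is 0.980. At d = 0.625 the SE is 0.0321, the test statistic shifts by −0.623, and rejection is 0.0261.

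| p | Null RR (k = 2) | Rejection, d = 0.9 to 0.625 |
|---|---|---|
| 0.1% | 0.998 | 0.0101 |
| 0.5% | 0.990 | 0.0133-0.0137 |
| 1% | 0.980 | 0.0240-0.0261 |

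With k = 1 (errors unrelated to prognosis) the RR is 1.000 and rejection is 0.0100 at every p.

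**Step 4: power under each grouping.** Now a fraction p is misallocated in each arm and the true RR is 0.88. The T+O group rate is (1 − q)·0.748 + q·0.85, and the Tio 5 group rate is (1 − q)·0.85 + q·0.748. Here q is the share of a group's time on the other drug:

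- wrong drug all year: q = p as randomised, 0 as first received;
- only the Visit 2 kits wrong (about 90 of 360 days): q = 0.25p as randomised, 0.75p as first received.

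Power points lost, over both dispersions and both values of T:

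| Case | Grouping | 0.1% | 0.5% | 1% |
|---|---|---|---|---|
| Wrong all year | as randomised | 0.10-0.16 | 0.52-0.83 | 1.07-1.69 |
| Wrong all year | first received | 0 | 0 | 0 |
| Visit 2 kits only | as randomised | 0.03-0.04 | 0.13-0.20 | 0.26-0.41 |
| Visit 2 kits only | first received | 0.08-0.12 | 0.39-0.62 | 0.79-1.25 |

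The last row assumes that the meeting leaves the default in place. Such patients are themselves switchers, so the SAP does not guarantee it.

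**Key secondary test, wrong drug all year, as randomised.** Take hazard ratio exp[ln 0.88·(1 − 2p)] and a control event proportion of 0.65. Schoenfeld power falls from 97.1% to 97.0%, 96.8% and 96.4% at the three rates.

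**The case against.** The strongest reply is that nothing is shown to be threatened. The sponsor is to "prepare and code the medication in a blinded fashion", and the IRT assigns kits by number, so an error should not depend on which drug the kit holds. Step 2 then gives nominal type I error. Inflation needs errors that are both one-directional and tied to prognosis, which blind coding makes implausible. Grouping by randomised arm can also cost power where first received costs none. The meeting is blinded, misallocations are logged, and no patient is dropped. All of this stands, and it is why the point is minor.

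Four stronger readings are tempting but unsupported:

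- **That the SAP contradicts the protocol.** Protocol 7.3.1 sets the analysis set and is silent on the arm, so there is no protocol arm rule to breach.
- **That the meeting lets results steer the grouping.** Scenarios are discussed blind and the decisions applied after lock. The defect is incomplete pre-specification.
- **That forced randomisations are misgrouped.** The IRT assigns and keeps the treatment these patients receive, so first received and final assignment agree.
- **That power argues for one grouping throughout.** Step 4 shows that the order depends on how long the wrong drug is taken.

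Redacted text also limits the claim. The SAP 6.1 table lists a sensitivity analysis of the primary endpoint over the planned treatment period, which visible SAP 7.4 does not describe, and parts of the SAP are blacked out. A grouping sensitivity analysis may already exist there. That would not change the visible rule for the main tests.

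**Conclusion.** The point holds as a minor one. SAP 6.1 is the only visible text that decides the arm in the two confirmatory tests. It chooses first treatment received and leaves switchers, possibly including those with wrong kits at later visits, to a meeting. No validity problem is expected: with blinded errors, type I error stays at 0.01. The figures above 0.01 in step 3 rest on an assumed misallocation rate, an assumed doubling of risk, and errors all in one direction. They bound an unlikely case and do not predict what will happen.

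The case for change is that the randomised arm is available, protects the comparison without an assumption about why errors occur, and can be written down now. Separately, SAP 6.1 and SAP 7.8.1 give different groupings for adverse events and need to be reconciled.

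**What to change.** Before unblinding, amend SAP 6.1:

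1. Analyse all efficacy endpoints, within the treated set, by randomised arm. Define this as the treatment linked to the patient's final IRT assignment at Visit 2. For forced randomisations, that is the treatment the IRT assigned and kept, not the one originally drawn but unavailable.
2. Remove the meeting's power to change the efficacy grouping.
3. Run first treatment received as an efficacy sensitivity analysis, unless redacted text already provides one.
4. Report how many patients had a first kit that differed from their arm, as a breakdown of violation C1.
5. State one safety grouping and bring SAP 6.1 and 7.8.1 into line with it.

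The cost is a few sentences and at most one extra model run, with no change to data collection, analysis set or sample size. The downside is the dilution in step 4 if misallocated patients stay on the wrong drug all year. If only the Visit 2 kits are wrong, the change loses less power than first received would, provided the meeting would have left the default in place.

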## 6.2 IMPORTANT PROTOCOL VIOLATIONS

A patient’s deviation from the trial protocol is considered “important” if it can be expected that the deviation had a distorting influence on the assessment of the treatment effect on the primary endpoint of the trial or could affect the patient’s safety/rights.

If the Interactive Response Technology (IRT)-assigned randomized medication is not available at the site at the first visit, a forced randomization will occur, and the IRT will assign a treatment that is available at the site. That patient will be assigned within the IRT system to receive that same treatment for the remainder of the trial. Forced randomizations

are part of the study plan and are not classified as important protocol violations. The number of forced randomizations will be closely monitored and described in the clinical trial report.

Table 6.2: 1 Important protocol violations

Category/ Code	Description	Example/Comment	Excluded from	Automatic /Manual
A	Entrance criteria not met			
A1	Inclusion criteria not met	IC 3, 4, 5, 7, 8, 2, 6,	None	Automatic and manual
A2	Exclusion criteria not met	EC 3, 7, 9, 10, 11, 13, 14, 15, 17, 23, 5, 6, 1, 4, 8, 2, 12, 16, 18, 19, 20, 21, 22	Excluded from TS: EC 22 Excluded from none: EC 1-21, 23	Automatic
B	Informed consent			
B1	Informed consent to study not available/not done*		All	Manual
B2	Informed consent too late**		None	Manual
C	Trial medication and randomization			
C1	Incorrect trial medication taken		None	Manual
C2	Randomization order not followed	Date of first trial drug intake prior to randomization date	None	Automatic
C3***	Serious non-compliance with study medication as reported in monitoring report	Decision at BRPM/MQRM.	None	Manual
C4	Medication code broken inappropriately		None	Manual
D	Concomitant medication			
D2	Prohibited medication use during study	Refer to Table 4.2.2.1: 1 in revised CTP.	None	Manual
Z	Other			
Z1	Serious Good Clinical Practice (GCP) non-compliance	Manual PVs reported by CML/CRA or in the GEM system.	None	Manual
Z2	Other PV affecting efficacy and possibly safety		None	Manual

\* Informed consent date missing; no signature on ICF.

\*\* Applies to all informed consents. Date of informed consent was after the date of any study-related procedure.

\*\*\* “Serious non-compliance with study medication” is defined by compliance  $\geq 200\%$  (twice the dose or more).

**Note:** The following IPV's are not programmed and should therefore be identified at site level on the manual PV log: B1, B2, C1, C3, C4, D1, D2, Z1, and Z2.

